### **8.6.3 Summaries of Baseline Characteristics, Demographics, and Other Analyses**

#### **8.6.3.1 Demographic and Baseline Characteristics**

The number and percentage of subjects screened, randomized/allocated, the primary reasons for screening failure, and the primary reason for discontinuation will be displayed. Demographic variables, baseline characteristics, primary and secondary diagnoses, and prior and concomitant therapies will be summarized either by descriptive statistics or categorical tables for ASaT population (by Arm), the set of subjects treated with the MK-1248 Recommended Phase 2 Dose (RP2D), and the set of subjects treated with the RP2D for combination of MK-1248 with pembrolizumab.

#### **8.6.3.2 Population PK Analyses**

Serum concentrations of MK-1248 in the MK-1248 arm and serum concentrations of MK-1248 and pembrolizumab in the MK-1248 administered with pembrolizumab arm will be summarized by planned visit and time for each dose separately; PK parameters will be summarized by dose. Descriptive statistics will be provided for each dose with at least 3 subjects; for other doses, the results will be listed.

The data from the study will be used to quantitatively explore the relationships among pharmacokinetics, target engagement, exploratory biomarkers and tumor response measurements.

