#### 3.2 Secondary Objective(s)

- 1) **Objective:** To characterize the PK profile of MK-1248 alone and in combination with pembrolizumab
- 2) **Objective:** To characterize the PK profile of pembrolizumab following administration of MK-1248 and pembrolizumab in combination
- 3) **Objective:** To evaluate target engagement as measured by modulation in peripheral blood GITR receptor availability alone and in combination with pembrolizumab

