### 5.2.1.2 Dose Escalation

In Arm 1 (MK-1248 monotherapy), dose escalation will begin with 0.12 mg in cohorts of 2 subjects each, and will proceed based on safety events to a dose of 10 mg. Starting at a 30 mg dose (or at a lower dose as described in Section 5.2.1.3) in Part B, dose escalation will continue with a 3+3 design to identify a preliminary maximum tolerated dose (MTD). In Part C, dose confirmation will refine the estimate of the tolerability of the MTD (or maximum administered dose), using a toxicity probability interval [1].

Enrollment to Arm 2, (MK-1248 in combination with pembrolizumab) will begin once 2 subjects complete 1 cycle of MK-1248 monotherapy at the  $\geq 3$  mg dose level in Part A, and will follow a 3+3 design to identify a preliminary MTD in Part D. The starting dose of MK-1248 will be 0.12 mg. Doses of MK-1248 will be escalated as described in [Table 3](#) and the dose of pembrolizumab will be fixed at 200 mg. Dose confirmation in Part E will refine the estimate of tolerability of the MTD using a toxicity probability interval [1].

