### 5.2.1.3 Accelerated Dose Escalation (MK-1248 Monotherapy)

During the accelerated dose escalation stage (Part A), each cohort will enroll two subjects and dose escalation will proceed as designated in [Table 2](#) and [Table 3](#), until a DLT is observed or until the dose level of 10 mg is safely administered. At least 2 days of observation will occur between each of the first 2 subjects at each dose level.

If a DLT is observed during a 2-subject cohort, an additional subject will be enrolled at this dose level for a total of 3 subjects, and the rules of 3+3 dose escalation described in Section 5.2.1.4 will apply:

- If the new subject does not develop a DLT (for a total of 1/3 subjects with a DLT at that dose level), three more subjects will be enrolled at this dose level and the rules of 3+3 design (Section 5.2.1.4) will be followed for a cohort of 6 subjects. The 3+3 dose escalation design will be followed from then on with 40% increments in the dose level.
- If the new subject develops a DLT (for a total of 2/3 subjects with a DLT at this dose level), the dose escalation stage of the trial will be terminated. The third subject will be enrolled in the dose directly below the current dose and the 3+3 dose escalation design will be followed from then on with 40% increments in the dose level.

See Section 5.2.2 for definition of DLTs.

Starting with the 30 mg dose, 3 subjects will be enrolled to each dose level.

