### **8.9 Sample Size and Power Calculations**

#### **8.9.1 Dose Escalation and Dose Confirmation**

The primary purpose of the dose escalation and dose confirmation parts of the trial is to investigate the safety and tolerability of MK-1248 monotherapy and MK-1248 co-administered with pembrolizumab in adult subjects with advanced solid tumors (Parts A-E) and to establish RP2Ds for MK-1248 monotherapy and MK-1248 co-administered with pembrolizumab.

The final number of subjects enrolled in the dose escalation and confirmation parts of the study will depend on the empirical safety (DLT) observations, in particular, at what dose the 3+3 design is triggered and what dose is identified as the RP2D. Sample sizes for a few possible scenarios as well as the estimated time required to enroll all subjects and the time

required to determine the MTD are provided below. The time required to estimate the MTD is the time from the first subject's first dose to the end of the 3-week observation period following the first dose of the last subject enrolled in the dose confirmation part. The study duration is derived as the time from the first subject's first dose to the end of 2-year treatment period following the enrollment of the last Part E subject.

The enrollment time was conservatively estimated assuming that during dose acceleration part it will take 4 weeks to proceed from one dose to the next and during 3+3 parts and that during the dose confirmation a subject can be enrolled every week.

Scenario 1. No DLTs during Parts A-E. For MK-1248 monotherapy, in a scenario where no DLTs are encountered during the dose escalation and confirmation parts and thus Part B continues to the highest dose in [Table 2](#), the sample size across Parts A-C is 46 subjects (8 subjects in Part A, 27 subjects across 9 doses in Part B, and 11 subjects on RP2D in Part C). For MK-1248 with pembrolizumab, in a scenario where Arm 2 starts at 0.12mg MK-1248 and 200 mg pembrolizumab and no DLTs are encountered during the dose escalation and confirmation parts so that Part D continues to the highest dose in [Table 2](#), the sample size across Parts D and E is 50 subjects (39 subjects across 13 doses in Part D, and 11 subjects on RP2D in Part E). The total sample size across Parts A-E is 96 subjects.

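### The PK section plans no estimate of MK-1248 exposure in combination versus alone; a dose-stratified joint analysis of the data already planned would supply one

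*Combined protocol and SAP*

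**What the plan says.** Section 3.2 sets two PK objectives: "To characterize the PK profile of MK-1248 alone and in combination with pembrolizumab" and "To characterize the PK profile of pembrolizumab following administration of MK-1248 and pembrolizumab in combination".

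Section 8.6.3.2 states that serum concentrations "will be summarized by planned visit and time for each dose separately; PK parameters will be summarized by dose", and then: "Descriptive statistics will be provided for each dose with at least 3 subjects; for other doses, the results will be listed". The section ends: "The data from the study will be used to quantitatively explore the relationships among pharmacokinetics, target engagement, exploratory biomarkers and tumor response measurements". That sentence names no model, covariate or arm effect. The SAP summary in section 8.1 repeats the by-dose approach.

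The group sizes follow from the design. In Part A, "each cohort will enroll two subjects" (section 5.2.1.3). Scenario 1 in section 8.9.1 gives Arm 1 as "8 subjects in Part A, 27 subjects across 9 doses in Part B, and 11 subjects on RP2D in Part C", and Arm 2 as 39 subjects over 13 doses plus 11 at the RP2D. Under section 5.2.1.5 the confirmed dose reaches 14 subjects, counting those from escalation. In Arm 2, "the dose of pembrolizumab will be fixed at 200 mg".

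**The concern.** The section heading suggests a joint model, but the text describes each dose in isolation. A reader wanting to know whether pembrolizumab shifts MK-1248 exposure would have to compare tables by eye, mostly with 3 subjects a side. At the four lowest doses the monotherapy side would be a listing of 2 subjects, set against an Arm 2 summary of 3.

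Tables 2 and 3 propose the same 13 MK-1248 dose levels for both arms. The arm contrast can therefore be formed within each dose and combined over doses, using subjects whose PK sampling is already planned. Section 4.2.3.3 says the PK results will help assess future dosing strategies, so a usable estimate has practical value.

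Pembrolizumab raises a related point. Every Arm 2 subject is assigned 200 mg, but the instruction to summarize each dose separately does not say whose dose is meant. Read as MK-1248 dose, it divides up to 50 like-dosed subjects into groups of mostly 3.

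**Working it through.** **Plan's own figure.** Arm 1: 4×2 + 9×3 + (14−3) = 46. Arm 2: 13×3 + (14−3) = 50. Total 96, as section 8.9.1 states. The documents give no PK precision, power or CV to reproduce.

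**Assumptions.** Log-normal exposure with between-subject CV of 40%, range 30-60%, so σ = √ln(1+CV²) = 0.385 (0.294 to 0.555). The arm ratio and σ are the same at every dose, and every subject has evaluable PK.

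**One dose.** 95% CI factor = exp[t(0.975, n1+n2−2) × σ × √(1/n1+1/n2)].
- 3 v 3, CV 40%: exp(2.776 × 0.385 × 0.816) = 2.39.
- 14 v 14, CV 40%: exp(2.056 × 0.385 × 0.378) = 1.35.

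**Combined within dose, Scenario 1.** Each dose contributes information n1·n2/(n1+n2).
- Four doses at 2 v 3: 4 × 1.2 = 4.8.
- Eight doses at 3 v 3: 8 × 1.5 = 12.
- One dose at 14 v 14: 7.
- Sum 23.8; df = 96 − 13 − 1 = 82. Factor at CV 40%: exp(1.989 × 0.385 / √23.8) = 1.17.

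**Combined, enrollment stopped before confirmation.** The number reached is not stated, so these cases are assumed.
- 4 shared doses at 2 v 3: N = 20, information 4.8, df 15.
- 10 shared doses (six more at 3 v 3): N = 56, information 13.8, df 45.

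**Pembrolizumab geometric mean in Arm 2.** Factor = exp[t(0.975, n−1) × σ/√n].

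| 95% CI factor | CV 30% | CV 40% | CV 60% |
|---|---|---|---|
| MK-1248 ratio, 3 v 3 | 1.95 | 2.39 | 3.52 |
| MK-1248 ratio, 14 v 3 | 1.49 | 1.69 | 2.12 |
| MK-1248 ratio, 14 v 14 | 1.26 | 1.35 | 1.54 |
| MK-1248 ratio, combined, 46 v 50 | 1.13 | 1.17 | 1.25 |
| Combined, 4 shared doses | 1.33 | 1.45 | 1.72 |
| Combined, 10 shared doses | 1.17 | 1.23 | 1.35 |
| Pembrolizumab mean, n = 3 | 2.07 | 2.60 | 3.96 |
| Pembrolizumab mean, n = 50 | 1.09 | 1.12 | 1.17 |

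**Half-width is not detectable difference.** At CV 40% with all 96 subjects the CI factor is 1.17, but the ratio detectable with 80% power is 1.25. For a true 2-fold ratio, power is 39% at 3 v 3 (59% at CV 30%, 22% at CV 60%). At 14 v 14 it is 89% even at CV 60%.

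**The case against.** The strongest reply is that the objectives ask only to characterize PK. They set no interaction hypothesis, margin or power requirement, and by-dose description with exploratory modelling left open satisfies that wording. This stands: the plan is under-specified and inefficient here, but it does not fail a stated requirement.

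Several stronger readings are tempting, and the documents do not support them.
- **That a 2-fold change in MK-1248 exposure would go unseen.** This is a fair worry at a 3 v 3 dose. It is not one at the confirmed dose when both arms confirm the same level, as in Scenario 1, because 14 v 14 would show it. If the arms confirm different doses, the comparison falls to 14 v 3, with 75% power at CV 40%. Cohorts with 1 DLT in 3 grow to 6, and section 5.2 allows up to 14 at a lower active dose.
- **That pooling resolves 17%.** That is a CI half-width under an assumed CV and full enrollment. Section 7.1.4.1 also lets the sponsor reduce PK sampling and analyze samples only if required.
- **That pooled data would show whether MK-1248 changes pembrolizumab exposure.** There is no pembrolizumab-alone arm, so no with/without ratio exists within the trial.
- **That pembrolizumab PK will certainly be split into 13 groups.** The wording also permits one 200 mg summary; it needs clarifying.

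The pooling assumptions deserve respect. Dose as a factor deals with non-proportional means, but not with an arm ratio that changes with dose, and section 4.2.2.1 reports non-linear PK in monkeys at lower doses. The dose levels are only proposed. Intermediate doses or a 40% ladder in one arm would leave some levels unmatched, and those add nothing to the within-dose contrast.

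**Conclusion.** The point holds as a cheap improvement. No estimate of MK-1248 exposure in combination versus alone is planned, and the exploratory sentence does not supply one. Without a DLT, the Part A monotherapy doses enter no comparison.

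The gain from a joint analysis is large beside a typical escalation dose (factor 2.39 down to 1.17 at CV 40%) and moderate beside a shared confirmed dose (1.35 down to 1.17). The 1.17 needs full Scenario 1 enrollment. With recruitment closed on 31-Mar-2017 at an unstated number, 1.23 to 1.45 is a more cautious range at CV 40% for 4 to 10 shared doses. If confirmation was not reached, the by-dose plan leaves mostly groups of 2 or 3, which makes pooling more useful rather than less.

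All factors rest on an assumed CV, a common arm ratio and evaluable PK in every subject. For pembrolizumab the gain is a more precise Arm 2 mean (2.60 at n = 3, 1.12 at n = 50, CV 40%) and a view of any trend over MK-1248 dose.

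**What to change.** Keep the by-dose summaries and listings, and add to section 8.6.3.2 text along these lines:

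> Log-transformed Cycle 1 MK-1248 PK parameters will be analyzed jointly over both arms at the dose levels they share, with dose level as a factor and arm as a term. The geometric mean ratio (combination/alone) will be reported with its 95% CI. A plot of exposure by dose and arm will be used to check whether a common ratio is reasonable. Pembrolizumab concentrations and PK parameters at 200 mg will be summarized over all Arm 2 subjects and also by MK-1248 dose, with the trend over MK-1248 dose.

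Dose as a factor avoids assuming dose proportionality and lets the 2-subject monotherapy doses contribute. The report should state how many shared dose levels and evaluable subjects the ratio rests on. It should also say that allocation to arms was non-random, and that the pembrolizumab results are not an interaction estimate.

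The cost is one SAP paragraph and one model, with no new samples or visits. The downside is the common-ratio assumption. If the plot contradicts it, the by-dose results remain the primary description.

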### **8.7 Interim Analyses**

No interim analyses are planned for this study.

### **8.8 Multiplicity**

There will be no multiplicity control in this study.

### **8.9 Sample Size and Power Calculations**

#### **8.9.1 Dose Escalation and Dose Confirmation**

The primary purpose of the dose escalation and dose confirmation parts of the trial is to investigate the safety and tolerability of MK-1248 monotherapy and MK-1248 co-administered with pembrolizumab in adult subjects with advanced solid tumors (Parts A-E) and to establish RP2Ds for MK-1248 monotherapy and MK-1248 co-administered with pembrolizumab.

The final number of subjects enrolled in the dose escalation and confirmation parts of the study will depend on the empirical safety (DLT) observations, in particular, at what dose the 3+3 design is triggered and what dose is identified as the RP2D. Sample sizes for a few possible scenarios as well as the estimated time required to enroll all subjects and the time

required to determine the MTD are provided below. The time required to estimate the MTD is the time from the first subject's first dose to the end of the 3-week observation period following the first dose of the last subject enrolled in the dose confirmation part. The study duration is derived as the time from the first subject's first dose to the end of 2-year treatment period following the enrollment of the last Part E subject.

The enrollment time was conservatively estimated assuming that during dose acceleration part it will take 4 weeks to proceed from one dose to the next and during 3+3 parts and that during the dose confirmation a subject can be enrolled every week.

Scenario 1. No DLTs during Parts A-E. For MK-1248 monotherapy, in a scenario where no DLTs are encountered during the dose escalation and confirmation parts and thus Part B continues to the highest dose in [Table 2](#), the sample size across Parts A-C is 46 subjects (8 subjects in Part A, 27 subjects across 9 doses in Part B, and 11 subjects on RP2D in Part C). For MK-1248 with pembrolizumab, in a scenario where Arm 2 starts at 0.12mg MK-1248 and 200 mg pembrolizumab and no DLTs are encountered during the dose escalation and confirmation parts so that Part D continues to the highest dose in [Table 2](#), the sample size across Parts D and E is 50 subjects (39 subjects across 13 doses in Part D, and 11 subjects on RP2D in Part E). The total sample size across Parts A-E is 96 subjects.

It will take 16 weeks to enroll and observe for DLTs the 8 MK-1248 monotherapy subjects in Part A and proceed to Part B enrolment; it will take additional 88 weeks to enroll 88 subjects (38 in Parts B and C and 50 in Parts D and E). Thus, in this scenario the enrollment time across Parts A-E is 104 weeks and the time required to determine the two MTDs is 107 weeks. The study duration then is approximately 104 weeks + 2 years or 4.0 years.

If dose escalation stops at a dose below the highest dose for either arm, the study might require less than 96 subjects and the enrollment duration shorter than 120 weeks. For example, if, in absence of DLTs, it is decided based on >95% receptor occupancy in tissue samples for multiple consecutive dose levels to stop MK-1248 escalation at 330mg dose and not explore the top three MK-1248 doses in Parts B and D, the sample size across Parts A-E will be 96-18=78 subjects. The enrollment duration will be 104-18=86 weeks and the total study duration will be 86 weeks+2 years or 3.6 years.

Also, with no DLTs observed, it might be possible to enter Part C and Part E subjects faster than one subject every week which will shorten the study duration.

Scenario 2: Flat DLT dose response. Suppose no DLTs are observed in Part A, and dose escalation in Parts B and D continues to the highest dose with flat dose response so that in Arm 1, 4 dose levels are studied in 3 subjects each and 5 dose levels (including the top one) are studied in 6 subjects each in Part B, while in Arm 2, 6 dose levels are studied in 3 subjects each and 7 dose levels (including the top one) are studied in 6 subjects each in Part D. Also suppose that the top dose is confirmed as the RP2D dose without de-escalation in Parts C and E. Thus, the sample size in Arm 1 is 58 subjects (8 in Part A, 42 in Part B, and 8 in Part C) and the sample size in Arm 2 is 68 subjects (60 in Part D and 8 in Part E). Total sample size is 118 subjects.

It will take 16 weeks to enroll 8 MK-1248 monotherapy subjects in Part A and proceed to Part B enrolment; it will take additional 118 weeks to enroll 118 subjects (50 in Parts B and C, and 68 in Parts D and E). Thus, in this scenario the enrollment time across parts A-E is

134 weeks and the time required to determine the two MTDs is 137 weeks. The study duration then is approximately 137 weeks + 2 years or 4.6 years.

Any dose de-escalations in Part C will increase the sample size in this example.

Scenario 3. Early start of 40% dose increments for Arm 2. If in Arm 2, 40% increments in the 3+3 design doses are triggered at 3 mg dose and dose escalation continues in 18 steps to 915 mg dose, with 3 subjects per dose in 3+3 design and 11 subjects in Part C, the sample size of Arm 2 across Parts D and E is 65 (54 in Part D and 11 in Part E). Suppose that dose escalation in Arm 1 proceeds without DLTs as in Scenario 1, and thus, the sample size of Arm 1 across Parts A-C is 46 subjects (8 subjects in Part A, 27 subjects across 9 doses in Part B, and 11 subjects on RP2D in Part C). The total sample size across Parts A-E is 111 subjects.

It will take 16 weeks to enroll 8 MK-1248 monotherapy subjects in Part A and proceed to Part B enrolment; it will take additional 103 weeks to enroll 103 subjects (38 in Parts B and C and 65 in Parts D and E). Thus, in this scenario the enrollment time across Parts A-E is 135 weeks and the time required to determine the two MTDs is 122 weeks. The study duration then is approximately 125 weeks + 2 years or 4.3 years.

The plausible sample size of approximately 96 subjects and the enrollment time of 104 weeks (study duration of 4 years) that correspond to the first described scenario are used for operational purposes.

### 8.9.2 Precision of the DLT rate at RP2D

The TPI design [1] will be used at the dose confirmation stage. This design assumes the toxicity rate at each dose level follows a beta-binomial hierarchical model. Based on the distance between the toxicity rate of the current dose and a pre-specified targeted toxicity rate, it assigns the current dose level to one of three toxicity intervals (i.e. under-dosing interval, proper-dosing interval, and over-dosing interval), which recommend actions of escalating, staying, or de-escalating the dose level, respectively. One of its attractive properties is that all possible dose-escalation decisions for a given trial can be pre-calculated, and tabulated in a spreadsheet, thus allowing investigators to easily implement and monitor the trial without subsequent statistical input. The dose confirmation rules using TPI design for this trial are presented in [Table 4](#), Subsection 5.2.1.5.

Since the TPI approach will be used during the dose confirmation Parts C and E, the estimated DLT rate, and its 95% Bayesian Probability Interval (PI) will be calculated from the posterior distribution of the DLT rate at RP2D using the model specified in the TPI approach. A uniform distribution between 0 and 1 is used as the prior when calculating the PIs in [Table 10](#). If 14 subjects are finally dosed at RP2D during the dose confirmation stage, the estimated DLT rate and its 95% PI should be similar to one of the rows in [Table 10](#).

Table 10 Precision of the estimated DLT rates at RP2D

Number of Subjects dosed at RP2D	Number of DLT Events	Estimated DLT Rate	Lower Bound of 95% PI	Upper Bound of 95% PI
14	2	0.143	0.027	0.373
14	3	0.214	0.068	0.460
14	4	0.286	0.106	0.533
14	5	0.357	0.158	0.609

## 8.10 Subgroup Analyses and Effect of Baseline Factors

No subgroup analyses will be performed.

## 8.11 Compliance (Medication Adherence)

Drug accountability data for trial treatment will be collected during the study. Percent compliance with drug administration will be calculated for each subject for MK-1248 and pembrolizumab separately.

For MK-1248 and pembrolizumab, percent compliance will be calculated as following:

$$\text{Percent Compliance} = \frac{\text{Number of Doses Taken}}{\text{Number of Doses that Should have been Taken}} \times 100.$$

For MK-1248, “Number of Doses that Should have been Taken” will be calculated as the minimum of the two numbers: 4 and (1 plus the number (integer) of 3-week intervals that fit between the date of the first dose and the date of the last dose of MK-1248).

For pembrolizumab, “Number of Doses that Should have been Taken” will be calculated as 1 plus the number (integer) of 3-week intervals that fit between the date of the first dose and the date of the last dose of pembrolizumab.

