### **5.2.5 Timing of Dose Administration**

Study treatment may be administered up to 3 days before or 5 days after the scheduled Day 1 of each cycle, beginning in Cycle 3. Cycle 2 Day 1 may be administered up to 5 days after the scheduled day 1. In addition, dosing interruptions are permitted in the case of medical/surgical events or logistical reasons not related to study therapy (e.g., elective surgery, unrelated medical events, subject vacation, and/or holidays). Subjects should be placed back on study therapy within 2 weeks of the scheduled interruption, unless otherwise discussed with the Sponsor. The reason for interruption should be documented in the subject's study record.

In Arm 2, pembrolizumab will be administered first on Day 1 of each cycle, with administration of MK-1248 occurring approximately 30 minutes after completion of the pembrolizumab administration.

Based on preliminary safety information from the ongoing study, the Sponsor recommends that all subjects be prophylactically pre-medicated, 1.5 hours ( $\pm$  30 minutes) before infusion with MK-1248, with the following:

- (1) Dexamethasone, 8 mg intravenously;
- (2) Acetaminophen, 1000 mg orally; and
- (3) Loratadine, 10 mg orally.

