##### **7.1.8.2 Treatment Period**

Visit requirements are outlined in Section 6.0 - Trial Flow Chart. Specific procedure-related details are provided above in Section 7.1 - Trial Procedures.

After a screening phase of up to 28 days, eligible subject will be assigned to one of 2 Arms and a dose level of MK-1248 by IVRS. In Arms 1 and 2, MK-1248 treatment will be administered on Day 1 of each 21-day cycle for up to a maximum of 4 cycles. In Arm 2, pembrolizumab will be administered on Day 1 of each 21 day cycle for up to 24 months of treatment.

Subjects will be followed until confirmed disease progression, unacceptable adverse event(s), intercurrent illness that prevents further administration of treatment, investigator's decision

to withdraw the subject, subject withdraws consent, pregnancy of the subject, noncompliance with study treatment or procedure requirements, or administrative reasons.

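### The compliance denominator truncates 3-week intervals and ignores the permitted 3-day early window, so a subject who follows the protocol can score above 100%

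*Combined protocol and SAP*

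**What the plan says.** Section 8.11 prescribes a per-subject result: "Percent compliance with drug administration will be calculated for each subject for MK-1248 and pembrolizumab separately". The percentage is doses taken divided by doses that should have been taken. For MK-1248 that denominator is "the minimum of the two numbers: 4 and (1 plus the number (integer) of 3-week intervals that fit between" the first and last dose dates. For pembrolizumab it is 1 plus "the number (integer) of 3-week intervals that fit between the date of the first dose and the date of the last dose" of that drug, with no upper limit.

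Section 5.2.5 sets the permitted dosing days. From Cycle 3 the window runs "up to 3 days before or 5 days after the scheduled Day 1 of each cycle, beginning in Cycle 3". Cycle 2 may only be late: "Cycle 2 Day 1 may be administered up to 5 days after the scheduled day 1". Footnote 1 of the Section 6.0 flow chart repeats both windows. Section 7.1.8.2 gives the planned MK-1248 course: "MK-1248 treatment will be administered on Day 1 of each 21-day cycle for up to a maximum of 4 cycles". For pembrolizumab it allows up to 24 months of 21-day cycles.

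Section 8.11 does not mention the window, does not limit the result to 100%, and does not say whether days between doses are counted inclusively.

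**The concern.** An integer number of intervals that fit between two dates is naturally read as whole intervals, with any remainder dropped. The formula therefore works only if the last dose is on or after its nominal day. Section 5.2.5 expressly allows it to be earlier. A last dose inside the permitted window can then cost one expected dose and push the ratio above 100% for a subject with no deviation.

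What is at stake is the credibility of a tabulated per-subject result. Values above 100% are impossible as adherence, and they raise any mean taken over subjects. Because MK-1248 has at most four doses, losing one from the denominator moves the percentage a long way.

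**Working it through.** The plan states no compliance percentage, so there is no published figure to reproduce. The formula was applied to dosing calendars that Section 5.2.5 permits.

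**Inputs**
- Expected doses E = 1 + floor(D/21), where D is days from first to last dose. For MK-1248, E is at most 4 (Section 8.11).
- Compliance = doses taken / E × 100 (Section 8.11).
- Windows: Cycle 2, 0 to +5 days; Cycle 3 onward, −3 to +5 days (Section 5.2.5).
- First dose on Day 1, so D = last dose day − 1.

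**Check on schedule.** For 1, 2, 3 and 4 doses given exactly on day, D = 0, 21, 42 and 63. Then E = 1, 2, 3 and 4, and every result is 100%.

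**Last dose early, MK-1248**
- Days 1, 22, 40: D = 39, floor(39/21) = 1, E = 2. Result 3/2 = 150%.
- Days 1, 22, 43, 61: D = 60, floor(60/21) = 2, E = 3. Result 4/3 = 133.3%.
- With cycle dates fixed from the first dose, 3 of the 9 permitted Cycle 4 days (−3, −2, −1) give 133.3%.

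**Last dose 3 days early, pembrolizumab.** The number of doses is not stated in the plan, so a range is shown.
- 6 doses: 6/5 = 120%
- 8 doses: 8/7 = 114.3%
- 20 doses: 20/19 = 105.3%
- 35 doses (assumed for 24 months): D = 34 × 21 − 3 = 711, floor(711/21) = 33, E = 34. Result 35/34 = 102.9%.

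**Where the artefact does not arise**
- Early middle dose, last dose on time (Days 1, 22, 40, 64): D = 63, E = 4, 4/4 = 100%.
- Last dose 5 days late, after 2, 3 or 4 MK-1248 doses: 100%.
- Cycle 2 given 5 days late, then Cycle 3 given 3 days early relative to that dose (Days 1, 27, 45): D = 44, E = 3, 3/3 = 100%.
- A dose skipped before the last one is detected (Days 1 and 43 only): D = 42, E = 3, 2/3 = 66.7%.

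**Sensitivity to the day count.** With an inclusive count, floor((D + 1)/21), a last dose 1 day early returns to 100%. A last dose 2 or 3 days early still gives 150% (three doses) or 133.3% (four doses).

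**Window-adjusted count.** Using E = 1 + floor((D + 3)/21):
- D = 39: floor(42/21) = 2, E = 3, 100%.
- D = 60: floor(63/21) = 3, E = 4, 100%.
- D = 711: floor(714/21) = 34, E = 35, 100%.

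This shortcut needs cycle dates fixed from the first dose. If each cycle instead rolls from the previous dose and every dose from Cycle 3 is 3 days early, four MK-1248 doses span D = 21 + 2 × 18 = 57. Then floor(60/21) = 2, E = 3, and 4/3 = 133.3% remains. Thirty-five pembrolizumab doses span D = 21 + 33 × 18 = 615. Then floor(618/21) = 29, E = 30, and 35/30 = 116.7% remains. Counting cycles rather than elapsed days avoids this.

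**The case against.** The strongest reply is that nothing depends on this number. Section 7.1.1.10 has both drugs given under the supervision of a qualified physician or designee. DLT evaluability has its own rule, at least 90% of the Cycle 1 infusion (Section 5.2.4). The MTD and RP2D rest on DLTs (Sections 5.2.1.5 and 8.9.2). A value of 133% is also easily recognised as an artefact. All of this stands and keeps the severity low, but it does not make a prescribed calculation correct.

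A reader might also infer three stronger points that the documents do not support.

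- *Any dose in the early window gives more than 100%.* It does not. Only the last dose date enters the formula, and an earlier delay can cancel the effect. The 1-day-early case further depends on a non-inclusive day count.
- *The formula is wrong because subjects who stop early score 100%.* It is true that one dose and no more gives 1/1 = 100%, against 1/4 = 25% of the planned MK-1248 course. But Section 5.8 requires stopping for progression, unacceptable toxicity and other reasons, so measuring adherence only while on treatment is a defensible definition. Early cessation is visible elsewhere: Section 8.12 reports doses received and Section 8.6.3.1 the primary reason for discontinuation. What remains is narrow: a subject removed for noncompliance after one dose would show 100% on this one measure.
- *Compliance is the plan's measure of whether the assigned doses were delivered.* Section 8.11 gives it no such role; Section 8.12 reports doses received.

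Running the count to the discontinuation date would bring its own error. Table 5 in Section 5.2.3.1 provides for MK-1248 to be held, with up to 12 weeks from the last dose for resolution. A subject held after one dose and discontinued at 12 weeks would score 1/4 = 25% while following the protocol.

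**Conclusion.** The formula is wrong as written, on a narrow point and with minor consequences. A protocol-compliant subject whose last dose falls just short of a whole multiple of 21 days after the first scores 150% after three MK-1248 doses or 133% after four. For pembrolizumab the excess shrinks as doses accumulate, to 103% at an assumed 35. The maximum of 4 limits the denominator, so it cannot prevent this.

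The conclusion rests on reading the integer count as whole intervals. Rounding to the nearest integer would remove these examples, but the wording does not suggest rounding. The results for a last dose 2 or 3 days early hold under either day-count convention; those for 1 day early need the non-inclusive count. How many subjects would be affected cannot be told from the documents. The measure is descriptive and no DLT, MTD or RP2D conclusion changes.

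**What to change.** In Section 8.11, define the doses that should have been taken as the number of scheduled cycle Day 1 visits from the first dose through the cycle of the last dose, matching each dose to its cycle with the Section 5.2.5 window, and keep the maximum of 4 for MK-1248. State whether cycle dates run from the first dose or from the previous dose. If they are fixed from the first dose, the definition reduces to 1 + floor((days from first to last dose + 3)/21).

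Because the count ends at the last dose, label the result as compliance while on treatment and present it alongside Section 8.12 exposure and the reasons for discontinuation. If the sponsor prefers to extend the count to the discontinuation date, cycles withheld under the protocol should be excluded from the denominator.

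The cost is a few sentences in the SAP and a small programming change, which can be made before database lock. It uses dosing dates the present formula already needs, plus each dose's cycle. Only the optional extension would also need discontinuation dates and a record of withheld cycles. No subject's treatment is affected.
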